**Design and Implementation of a Nutritional Intervention in
Patients With Oropharyngeal Dysphagia**

NCT02959450

October 10th, 2021

Statistical analysis

The data are presented as mean \pm standard deviation or median with interquartile range [25th- 75th percentile], depending of data distribution. The Shapiro-Wilk test for proper parametric or non-parametric test was performed. Differences between groups at baseline were evaluated with Student's t-test or U Mann-Whitney test for continuous variables and proportions were compared using the Chi2 or Fisher test. Two analyses were performed to evaluate the effect of the nutritional intervention: an intention-to-treat analysis (considering all of the participants) and per-protocol analysis (considering participants who finished the follow-up). Missing data were imputed with the multivariate imputation. For the intention- to-treat analysis, we imputed five complete data sets and pooled the results for the analysis. For post-intervention comparison within-groups, a paired Student-t or Wilcoxon matched-pairs signed rank tests were performed. Also changes between baseline and final intervention in oral intake, body weight and HGS were obtained between groups and were compared with the Mann-Whitney U test, according to the nonparametric distribution of the data. A p-value <0.05 was considered statistically significant. The data were analyzed using the Statistical Package for the Social Sciences (SPSS®) version 25.

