**Design and Implementation of a Nutritional Intervention in
Patients With Oropharyngeal Dysphagia**

NCT02959450

October 10th, 2021

Patients of 18 years and older, both genders, who had a primary caregiver and a confirmed diagnosis of OD were included. Eating Assessment Tool (EAT-10) and Volume- Viscosity Swallow Test (V-VST) were performed by a clinical nutritionist in order to evaluate the safety and efficacy of swallowing and confirm the diagnosis of OD; select the type of viscosity and volume appropriate for the prescription of the texture-modified diet. Patients with cancer, kidney or hepatic failure, terminally ill patients, as well as high risk of aspiration, reporting a decrease in oxygen saturation $>5\%$ in the V-VST, or with enteral nutrition (EN) through a nasoenteral tube or gastrostomy were excluded. We estimated a sample size of 50 patients per group by the formula of survival of Argimon et al , with an alpha level of 0.05 and more than 90% power to detect a difference of 15% of mortality between groups.

Anthropometry

Anthropometric measurements were performed according to the reference manual for anthropometric standardization. The same scale was used for all patients at each visit. Forearm circumference was measured at the midpoint of the right arm and calf circumference was measured in a supine position with the tape along the calf to measure the greatest circumference without compressing the subcutaneous tissue.

Mini Nutritional Assessment

The nutritional risk was assessed using the Mini Nutritional Assessment (MNA) questionnaire, a valid and reliable tool to identify malnutrition in elderly people. The original version of this tool was used for this study contained 18 questions with a maximum of 30 points. It is considered that a score lower than 17 points represents malnutrition, between 17 and 23.5 points of risk of malnutrition and more than 24 points that the patient is well nourished.

Dietary intake

For the evaluation of the quality and quantity of dietary intake, a 24-hour multiple-step recall was applied and the Food Processor Nutrition Analysis® software was used for the detailed nutritional analysis.

Body composition

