Subjects were randomly allocated to intervention group (modified consistency diet, with a nectar or pudding viscosity) or control group (standard treatment) using a blocked allocation strategy. The *control group* received a traditional modified texture diet, with pureed foods and one viscosity of thickened drinks. The viscosity beverages were not systematically controlled. For the *intervention group* a chef and a clinical nutritionist developed the texture- modified foods and thickened drinks diet, with nectar or pudding viscosity and controlled bolus volume. The foods were thickened using Enterex Food Thickener, Victus® and the viscosity of menus was standardized and measured with a Brookfield Viscometer (model RV). The menus with nectar consistency had a viscosity of 51-350 centipoises (cP) and the pudding consistency foods with a higher viscosity at 1,750 cP. The viscosity of the diet was prescribed according to the viscosity and volume tolerated in the V-VST. A recipe book for caregivers and patients was made to facilitate the preparation of the diet with the exact amount of thickener to use in each menu to achieve the desired viscosity. Training was also provided to patients and caregivers by a video on the use of food thickener (modified ediblestarch) on each menu.

The primary outcome was the amount of energy (kcal/kg) and protein (g/kg) consumed, the secondary outcome was body composition and muscular functionality. The follow-up was carried out in 5 visits during 12 weeks. Adherence to the prescribed meal plan was evaluated at each visit. To evaluate the adherence, it was necessary to have an intake of more than 80% of the nutritional requirements with 24-hour recall. If the intake was lower than indicated, oral nutritional supplements were prescribed to meet the nutritional requirements established in both groups.

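### With only five imputed data sets, a borderline intention-to-treat p-value for energy or protein intake can depend on the random seed

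*SAP*

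**What the plan says.** The SAP (Statistical analysis) plans two analyses, one of all participants and one of those who completed follow-up, and makes neither of them primary. On missing values it says "Missing data were imputed with the multivariate imputation", and for the intention-to-treat analysis "we imputed five complete data sets and pooled the results for the analysis". It names no imputation model, seed, expected missing fraction or pooling rule. Changes from baseline "were compared with the Mann-Whitney U test, according to the nonparametric distribution of the data". The decision rule is a fixed threshold: "A p-value <0.05 was considered statistically significant".

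The protocol (end of the Nutritional intervention section) gives two co-listed primary variables: "The primary outcome was the amount of energy (kcal/kg) and protein (g/kg) consumed". Follow-up is 12 weeks with five visits.

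**The concern.** Multiple imputation adds a random step to the analysis. With few imputed data sets, that randomness carries through to the pooled estimate, its standard error and the p-value. With five, the between-imputation variance is estimated on only 5 − 1 = 4 degrees of freedom, against 49 with 50. This makes the standard error unstable and the interval wider than the data require.

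Because the SAP judges results against a hard cut-off, a result close to it could be declared significant under one seed and not under another, with the same patients and the same model. Some power is also given up, although more imputations would cost almost nothing.

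**Working it through.** **Figures in the plan.** On this point there is only the number five. The one power statement, "We estimated a sample size of 50 patients per group by the formula of survival", rests on a mortality difference, so it gives no power for intake that could be reproduced here.

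**Inputs from the documents.** Five imputations, 50 per group, threshold 0.05.

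**Assumed inputs.** Missing final values 10–50%; true effect 0.5 SD, with 0.8 SD as an alternative; baseline-to-final correlation 0.5; two-sided testing; a mean difference pooled by Rubin's rules with small-sample degrees of freedom.

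**Step 1: seed noise in closed form.** Let W and B be the within- and between-imputation variances, m the number of imputations, and λ = B/(W + B) the fraction of missing information. Rubin's total variance is W + (1 + 1/m)B. Re-seeding moves the pooled estimate with variance B/m. In units of the full standard error, its SD is therefore √(λ/m).

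| λ | m = 5 | m = 50 |
|---|---|---|
| 0.1 | √0.020 = 0.14 | √0.002 = 0.04 |
| 0.2 | √0.040 = 0.20 | √0.004 = 0.06 |
| 0.3 | √0.060 = 0.24 | √0.006 = 0.08 |

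On the normal scale, p = 0.03 is z = 2.17 and p = 0.05 is z = 1.96, a gap of 0.21. With five imputations the seed noise is of the same order as that gap; with 50 it is well below it. This leaves out the further noise in the estimated standard error.

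**Step 2: p-value over seeds, data held fixed.** Simulation including the noise in the standard error gave the percentage of seeds with p<0.05:

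| Many-imputation p | λ | m = 5 | m = 50 |
|---|---|---|---|
| near 0.03 | 0.1 | 82% | 100% |
| near 0.03 | 0.2 | 67% | 99% |
| near 0.03 | 0.3 | 59% | 95% |
| near 0.01 | 0.1 | 99.7% | 100% |
| near 0.01 | 0.2 | 95% | 100% |
| near 0.01 | 0.3 | 87% | 100% |

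**Step 3: whole trials.** Final values were imputed from arm and baseline, with two independent imputation runs per data set, and analysed by ANCOVA (0.5 SD effect). Repeated runs of this simulation gave the following disagreement between seeds on p<0.05:

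| Missing | m = 5 | m = 50 |
|---|---|---|
| 10% | 6, 6.8% | 2, 2.2% |
| 20% | 11, 11.6, 11.9, 12.7% | 2.5, 2.8, 3, 3.6% |
| 30% | 16.8, 16.9, 17, 17.3% | 3.7, 4, 4.3, 4.7% |

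A t-test on change gave 6.5/10.6/14.7% with five and 1.6/2.6/3.8% with 50 at 10/20/30% missing, so the pattern does not depend on ANCOVA.

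**Step 4: power and interval width.**
- In two ANCOVA runs, power with 5 against 50 imputations was 66.5 v 70.3 and 68.2 v 71.6 at 20% missing (losses 3.8 and 3.4 points), and 57.6 v 62.4 and 59.7 v 64.9 at 30% (losses 4.8 and 5.2). A further run gave about 2 points at 20%.
- At 10% missing, the ANCOVA runs ranged from a loss of about 2 points to no detectable loss.
- For a t-test on change the losses were 0.6, 2.5 and 2.6 points at 10/20/30%. With complete-data power set near 80 or 90% and 100 imputations as comparator, they were 1.0/0.6 points at 10% missing, 1.8/1.8 at 20%, 3.9/3.2 at 30%, 6.6/5.8 at 40% and 8.8/7.5 at 50%.
- Mean 95% interval widths in one ANCOVA run were 0.809 v 0.782 at 20% missing (ratio 1.03) and 0.902 v 0.844 at 30% (ratio 1.07).

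**Step 5: larger effect.** At 0.8 SD, disagreement with five imputations falls to about 1–5% and the power loss to 0–3 points up to 30% missing. For example, at 20% missing the figures are 2.6% and 97.3 v 98.0. At 40% missing it is again material: 13.9% disagreement, and power 85.5 v 93.0.

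**Step 6: validity.** With five imputations the simulated type I error stayed near 5%.

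**The case against.** The usual defence of five imputations is relative efficiency, 1/(1 + λ/5): 0.98, 0.96 and 0.94 at λ = 0.1, 0.2 and 0.3. The arithmetic is right, but it describes the variance of the estimate. It does not describe the stability of the p-value or the few degrees of freedom behind the interval.

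Other objections have more force:
- A reader might infer that a fixed loss of some 4–6 power points has been shown. The documents do not support that. They give no dropout rate, effect size or SD for intake, and over the assumed range the loss runs from nothing detectable to about 11 points at λ = 0.5. An effect that gives middling power also puts many p-values near 0.05, which raises disagreement.
- A reader might infer that the trial's main conclusion is irreproducible. There is no single primary p-value: two intake variables are named and neither analysis set is ranked first. A recorded seed makes even a five-imputation result exactly repeatable. A p-value well below 0.05 is little affected when the missing fraction is modest.
- The simulations pool a mean difference, whereas the SAP specifies Mann-Whitney and does not say how it is pooled. The figures are therefore a stand-in. That gap may matter more than the number of imputations, and raising the number does not close it.
- Twenty imputations recover the power: 70.8/64.4% against 70.5/64.4% with 50, at 20/30% missing. They leave more seed disagreement, 5.0/7.7% against 2.8/4.7%, so the case for 50 rests on stability.

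**Conclusion.** The point stands as a minor, nearly free improvement. Five imputations give valid inference, with no bias or type I error inflation, but leave avoidable noise in any intention-to-treat result near the threshold. On the 0.5 SD assumptions, seed disagreement of roughly 6–17% at 10–30% missing falls to roughly 2–4% with 50 imputations. The power cost is about 0–2, 2–4 and 3–5 points at 10, 20 and 30% missing, and more above that; at 0.8 SD it is 0–3 points up to 30% missing.

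These sizes depend on the assumed missing fraction, effect, correlation and pooled mean difference, none of which the documents fix. The direction is the same throughout: more imputations make a borderline result less dependent on the seed.

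**What to change.** In the SAP (Statistical analysis), replace five with at least 50 imputed data sets and record the seed. The SAP is written in the past tense, so the analysis may already have been run. In that case, keep the five-imputation result, report the re-run with the larger number beside it, and label it as a later addition. The cost is one changed number, one added seed and trivial computing time for about 100 patients. How the Mann-Whitney comparisons are pooled needs its own statement; this change does not supply it.

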The body composition was performed using a single-frequency BIA (50-kHz, Quantum X, RJL Systems, Inc) with the standard technique: all participants were supine with limbs slightly spread apart from the body, refrained from eating, drinking, and exercising for six hours, no alcohol within 24 h before testing and portable electric heaters. The area was cleaned with alcohol and the electrodes (recommended by manufacturers RJL Systems, Inc) were placed on an imaginary line bisecting the ulnar head of the right hand and on an imaginary line bisecting the medial malleolus of the right finger and on the base of the second toe of the right foot. Finally, the R and Xc values were recorded. All measurements were performed under strictly standardized conditions by the observer, using the same device in order to avoid interobserver and interdevice variability. The Quantum X was calibrated periodically by a test resistor with a known value of 495 – 505 ohms of R to ensure accuracy of measurements. The coefficient of variation was reported in a range from 1.8 to 2.9%.

Muscle strength

The muscular functionality was evaluated by a handgrip dynamometer (Takei®). The operator, using the same device in order to avoid interobserver and interdevice variability, performed all measurements under strictly standardized conditions. For the measurement, subjects were placed standing with arms outstretched parallel to the trunk taking the dynamometer and applying maximum strength with each hand without support. The measurement was repeated three times with separation of 1 min to avoid fatigue and the maximum value was recorded. The instrument was routinely checked resistors and capacitors of known values.

Nutritional intervention

Nutritional requirements for both groups were calculated based on the American Society for Parenteral and Enteral Nutrition and Society of Critical Care Medicine (A.S.P.E.N./S.C.C.M.) and recommendations of PROT-AGE Study Group as follows: 25- 30 kcal/kg Body Weight (BW)/day in patients with body mass index (BMI) <30 kg/m² and 20-25 kcal/kg ideal BW/day with BMI > 30 kg/m²; protein were

calculated 1.2-1.5 g/kg

BW/day for patients with BMI <30 kg/m² and in case that BMI was >30 kg/m² protein were calculated 2 g/kg ideal BW/day in both groups. Both groups received swallowing rehabilitation (postural maneuvers, increase oral sensitivity, neuromuscular practices).

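### Within-arm paired tests are not marked as descriptive, and for body composition, a secondary outcome, they are the only post-intervention test described

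*SAP*

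**What the plan says.** The single SAP section, Statistical analysis, opens its account of the effect analyses with "Two analyses were performed to evaluate the effect of the nutritional intervention" and then names an intention-to-treat and a per-protocol analysis. After a description of imputation it gives two kinds of post-baseline test.

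- Within each arm: "For post-intervention comparison within-groups, a paired Student-t or Wilcoxon matched-pairs signed rank tests were performed". No outcomes are listed for these tests.
- Between arms: "changes between baseline and final intervention in oral intake, body weight and HGS were obtained between groups", compared by the Mann-Whitney U test.

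One threshold covers both kinds: "A p-value <0.05 was considered statistically significant". Neither comparison is named as primary, and the within-arm tests are not described as supportive or descriptive.

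The Protocol (Nutritional intervention) makes energy and protein intake the primary outcome, and body composition and muscular functionality secondary. It also describes care common to both arms:

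- "Both groups received swallowing rehabilitation (postural maneuvers, increase oral sensitivity, neuromuscular practices)".
- Energy and protein requirements were calculated by the same rules in both groups.
- The control arm "received a traditional modified texture diet, with pureed foods and one viscosity of thickened drinks".
- When intake fell below the adherence threshold, "oral nutritional supplements were prescribed to meet the nutritional requirements established in both groups".

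On timing: "The follow-up was carried out in 5 visits during 12 weeks".

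**The concern.** A paired test inside one arm asks whether that arm changed from baseline. Here the control arm is actively treated, so both arms may change over 12 weeks without any contribution from controlled viscosity. The supplement rule acts directly on the primary outcome, because it is triggered by low intake in either arm. A within-arm p-value mixes this shared care and the course of the dysphagia with any effect of the diet, and it makes no use of the randomised control. Finding one arm significant and the other not is not a test of the difference between them.

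The consequences differ by outcome. For oral intake, body weight and HGS, a reader could cite a significant change in the intervention arm even where the between-arm test is null, and nothing in the SAP says which result prevails. For body composition, no between-arm test of change is listed, so the plan as written supplies only the within-arm result.

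**Working it through.** **Step 1. Match outcomes to tests.**

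| Outcome (Protocol) | Within-arm paired test (SAP) | Between-arm test of change (SAP) |
|---|---|---|
| Energy and protein intake (primary) | yes | yes, as oral intake |
| Muscular functionality, by handgrip (secondary) | yes | yes, as HGS |
| Body composition, by bioimpedance (secondary) | yes | not listed |
| Body weight | yes | yes |

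The SAP's other between-group tests are for baseline differences. Body weight is listed, but it is not the bioimpedance measurement that the Protocol describes under Body composition.

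**Step 2. How often would the within-arm pattern mislead if someone relied on it?** The plan gives no figure of its own to reproduce here.

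Inputs from the documents: n = 50 per arm (Protocol, sample-size statement) and a 0.05 threshold (SAP). Assumptions: two-sided tests; normally distributed changes; the same true standardised change d (mean change divided by the SD of change) in both arms; no diet effect; independent arms.

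Formulas:

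- Noncentrality = d × √50; df = 49; critical t = 2.010.
- U = probability that an arm shows significant improvement; L = probability of significant worsening (noncentral t).
- P(significant improvement in the intervention arm only) = U × (1 − U − L).

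| d | U | 1 − U − L | Intervention arm only |
|---|---|---|---|
| 0 | 0.025 | 0.950 | 2.4% |
| 0.1 | 0.103 | 0.893 | 9.2% |
| 0.2 | 0.283 | 0.716 | 20.3% |
| 0.28 | 0.492 | 0.508 | 25.0% (maximum) |
| 0.4 | 0.792 | 0.208 | 16.5% |
| 0.5 | 0.934 | 0.066 | 6.2% |
| 0.7 | 0.998 | 0.002 | 0.2% |

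Worked line, d = 0.28: noncentrality 0.28 × 7.071 = 1.98; U = 0.492; L is negligible; 0.492 × 0.508 = 0.250. The maximum falls where within-arm power is about one half, since p(1 − p) peaks at 0.25.

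**Step 3. Simulation check.** At d = 0.28 with 50 per arm, the pattern occurred in 24.5% of trials with the paired t-test (10,000 trials) and 23.8% with the Wilcoxon signed rank test (2,000 trials). Across d from 0 to 0.5, the Mann-Whitney test of change between arms rejected in 4.6% to 5.2% of trials, which is its nominal two-sided level.

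**Step 4. Smaller arms.** With 35 per arm the pattern occurs in 16.5% of trials at d = 0.2, 25.0% at 0.35 and 23.2% at 0.4. The peak moves to a larger d but keeps its height.

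**The case against.** The strongest reply is that the randomised comparison is already in the SAP, in the sentence after the paired tests. It covers oral intake, which bears on the primary outcome, together with body weight and HGS. A reader who uses it keeps the nominal error rate: under no diet effect, the intervention-only pattern combined with a significant Mann-Whitney result occurs in 2.3% of simulated trials or fewer, for every d from 0 to 0.7. This stands, and for those three outcomes it reduces the issue to one of interpretation.

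Two stronger readings are tempting, and the documents support neither. First, a reader might infer that the SAP makes the within-arm tests its means of judging the effect, because it speaks of evaluating the effect and lists those tests first. But the sentence about the effect goes on to define the two analysis sets, order of mention is not a hierarchy, and nowhere does the SAP say that one arm's p-value will be set against the other's. Second, a reader might take 25% as the trial's false-positive rate. It is the error rate of a decision rule that the SAP does not state, at the least favourable d.

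Two further limits also stand. Supplements are conditional on low intake and are not given to every patient. Regression to the mean should not be pressed, because patients were selected on dysphagia and no entry threshold on intake, weight or handgrip is stated.

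None of this answers the body composition gap, or the absence of any statement on which comparison governs.

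**Conclusion.** The concern holds in a limited form. The firm part is body composition: a named secondary outcome whose only described post-intervention test is within-arm, so that following the SAP as written gives it no randomised comparison. This comes from the text and rests on no numerical assumption.

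For oral intake, body weight and HGS a valid between-arm test exists, and error arises only if conclusions lean on the within-arm p-values. The size of that error depends wholly on the shared change, for which the documents give neither an expected value nor an SD. It is negligible when the shared change is near zero or large, and substantial in the middle of the range. The point merits a correction to the SAP but does not invalidate the planned comparison for the primary outcome.

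**What to change.** In the SAP, Statistical analysis:

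1. Extend the between-arm comparison of change to body composition, naming the variable or variables tested, so that every primary and secondary outcome has a randomised comparison.
2. Report within-arm change from baseline with a 95% confidence interval, as description only and without p-values.
3. Add a sentence such as: Conclusions about the effect of the intervention rest only on the randomised between-group comparison of change; within-group changes are descriptive.

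The second and third changes need the first. Without it, removing the within-arm p-values would leave body composition with no stated post-intervention test.

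The cost is one added between-arm comparison and fewer significant results to report. Body composition is already measured, so no new data are needed.

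### Body composition is the only declared outcome for which the SAP specifies no between-group test

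*SAP*

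**What the plan says.** The outcome statement at the end of the protocol's Nutritional intervention section makes energy and protein intake primary, and adds that "the secondary outcome was body composition and muscular functionality". The protocol's Body composition section defines the method: "The body composition was performed using a single-frequency BIA", and "Finally, the R and Xc values were recorded". Muscular functionality is measured by handgrip dynamometer. Body weight belongs elsewhere, under Anthropometry: "The same scale was used for all patients at each visit".

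The SAP (Statistical analysis) compares the groups at baseline and tests before/after change within each group by paired t or Wilcoxon. For the comparison between arms after baseline it states that "changes between baseline and final intervention in oral intake, body weight and HGS were obtained between groups" and that these "were compared with the Mann-Whitney U test, according to the nonparametric distribution of the data". Intention-to-treat and per-protocol sets are defined without naming an outcome or a test. Missing data are handled by five pooled imputations.

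**The concern.** The SAP says its analyses are there to assess what the intervention did. In a randomised trial that calls for a comparison between arms. A before/after test within one arm mixes the diet's effect with natural course and with everything else both arms received. Here that is not a remote worry: "Both groups received swallowing rehabilitation", and patients in either arm could be prescribed oral supplements when intake fell short. Both arms may therefore change for reasons unrelated to the texture-modified diet.

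If the SAP is followed as written, a declared secondary outcome has no randomised comparison, while body weight, which is not a declared outcome, has one.

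**Working it through.** **Matching outcomes to tests.** The plan has no figure of its own to reproduce here, so the check sets the protocol's outcomes against the SAP's between-group list.

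| Declared outcome (protocol) | Measure | Between-group test of change (SAP) |
|---|---|---|
| Energy and protein intake (primary) | 24-hour recall | Mann-Whitney U, as oral intake |
| Muscular functionality (secondary) | Handgrip | Mann-Whitney U, as HGS |
| Body composition (secondary) | BIA, R and Xc | None stated |

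This takes oral intake to mean energy and protein, and HGS, which is not expanded, to mean handgrip strength. Mortality, which drives the sample size ("to detect a difference of 15% of mortality between groups"), is not a declared outcome and is left aside.

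**Inputs for the illustration.** From the documents: 50 per arm, alpha 0.05, five imputations. Assumed: two-sided tests, normal data, and effects in units of the SD of change, because no BIA SD is given.

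**Reading the two within-arm tests against each other.** Let d be the true improvement, the same in both arms. Let u be the probability that a paired t test (49 df, noncentrality d√50) is significant for improvement, and p the probability that it is significant in either direction. The chance of improvement in the intervention arm with a non-significant control arm is u(1 − p).

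| d (SD) | u | p | u(1 − p) |
|---|---|---|---|
| 0 | 0.025 | 0.050 | 0.024 |
| 0.10 | 0.103 | 0.107 | 0.092 |
| 0.20 | 0.283 | 0.284 | 0.203 |
| 0.28 | 0.492 | 0.492 | 0.250 |
| 0.40 | 0.792 | 0.792 | 0.165 |
| 0.50 | 0.934 | 0.934 | 0.062 |
| 0.60 | 0.986 | 0.986 | 0.014 |

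A direct two-sided between-arm test errs in that direction 2.5% of the time. The pattern exceeds 2.5% up to d = 0.56 (2.7%) but not at 0.57 (2.3%).

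**The opposite case.** Let control improve by 0.5 SD and intervention by 1.0 SD. Both within-arm tests are significant in 0.934 × 1.000 = 93% of trials, so the p-values do not distinguish the arms.

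**What a between-arm model would give.** Regress the final value on arm and baseline value. With equal variances at the two visits and baseline–final correlation r, the residual variance is (1 + r)/2 in squared SDs of change, so the standard error of the arm difference is √((1 + r)/50). With t = 1.985 (97 df), complete-data results are:

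| r (assumed) | SE | 95% CI half-width (SD) | Power for a 0.5 SD difference |
|---|---|---|---|
| 0.5 | 0.173 | 0.34 | 81% |
| 0.8 | 0.190 | 0.38 | 74% |
| 0.9 | 0.195 | 0.39 | 72% |

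Simulation (4,000 trials per setting) gave 80.1% at r = 0.5 and 73.4% at r = 0.8. With 20% of final values missing completely at random (assumed) and five imputations pooled by Rubin's rules, power was 66.8% and 60.2%, and half-widths were 0.41 and 0.44 SD. At r = 0.9, pooled power is about 58% to 59%. With equal change in both arms, the pooled test rejected in 4.6% to 5.1% of trials; interval coverage over all settings was 94.7% to 95.4%.

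**The case against.** The strongest reply is that this is loose reporting. The SAP uses Shapiro-Wilk to choose between parametric and non-parametric tests, and its between-group list is tied to non-normal data. It may name only the variables that failed that check, with BIA compared by a t-test. That is possible, and it is why the point is that a test is not specified, not that none was done. But the SAP ties Student's t-test to baseline and the paired t to within-group change. No parametric between-group test of change is stated.

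A second reply is that the SAP's three variables line up with the protocol's three outcome domains, so body weight may have been meant to stand for body composition. This cannot be excluded, but nothing says so. The protocol describes the two separately, and BIA would still be untested.

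Third, the 9% to 25% rates depend on a way of reading two p-values that the SAP does not state. That stands: they show what a misreading would cost, not an error rate of the plan. Likewise, in the opposite case unequal changes would be visible in the descriptive statistics, though untested.

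Finally, a baseline-adjusted model goes further than adding BIA to the existing sentence, and treats this outcome differently from the primary. That is true and is a cost. The reason for it is that the model yields an estimate and standard error that can be pooled over imputations.

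**Conclusion.** The concern holds. Body composition is a declared secondary outcome with no between-group test specified, and the only post-baseline test that could apply to it is the within-arm one. This follows from the text and needs none of the assumed figures.

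The practical size is uncertain. If the two within-arm results were read against each other, a false impression of benefit could arise in up to 25% of trials, depending on the common change. A real 0.5 SD difference could also go untested when both arms improve. These figures rest on normal data, 50 analysed per arm and the assumed effect sizes; the power figures also rest on the assumed correlations and missingness. The primary outcome is unaffected, so this should be corrected but does not undermine the trial's main comparison.

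**What to change.** Name the single BIA measure that represents body composition, and include it in the between-group comparison for both the intention-to-treat and per-protocol analyses. Estimate the arm difference with a linear model of the final value on arm and baseline value, and report it with a 95% CI. In the intention-to-treat analysis, pool the arm coefficient and its standard error over the five imputed data sets by Rubin's rules. Where data are non-normal, Mann-Whitney U on change can support the result, but it supplies no estimate or standard error to pool. State that within-group tests are descriptive.

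The cost is a short SAP addition and no new data. The model will differ from the test used for the other outcomes. It also adds one uncorrected comparison: counting energy and protein separately (assumed), between-group tests rise from 4 to 5. If they were independent with no true effects, the chance of at least one false positive per analysis set would go from 1 − 0.95⁴ = 18.5% to 1 − 0.95⁵ = 22.6%. Testing both R and Xc would make it 1 − 0.95⁶ = 26.5%, a reason to choose one measure. The SAP is written in the past tense; if the analysis is complete, label this comparison post hoc.
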